30 to classical methods. In SIRIUS we will prospectively challenge this hypothesis to address the
31 question of how often a better or final diagnosis can be delivered by WGS and/or WTS and if
32 unclear cases can be efficiently resolved.

33

34 **Type of Research:** observational study, diagnostic study, hematology, leukemia, next
35 generation sequencing

36

37 **Intervention:** none

38 **APPROVAL**

39 This study will be conducted with the utmost respect for individual patients in accordance with
40 the requirements of this diagnostic trial protocol and especially in accordance with the
41 following:

42 • Good clinical practice directive (European Union) (2005/28/EC)

43 • The ethical principles in accordance with the Declaration of Helsinki

44 • International Conference on Harmonization (ICH) E6 Good Clinical Practice:
45 consolidated guideline

46 • Guidelines for Good Clinical Practice (*Deutsche Forschungsgemeinschaft DFG*)

47 • Standards and guidelines for the interpretation of sequence variants (PMID: 25741868)

48 • All applicable laws and regulations, including, without limitation, data privacy laws,
49 clinical trial disclosure laws, and regulations.

50 **I. INTRODUCTION**

51 1. Background and Rationale

52 Treatment of hematological diseases relies on a single cardinal prerequisite: correct
53 classification within the broad specter of malignant diseases arising from the hematopoietic
54 system. With the ever-expanding availability of distinct yet complementary diagnostic tools,
55 our understanding of the landscape of hematological diseases steadily increases. As such, the
56 current consensus classification as summarized through the WHO classification (2017)
57 represents a compass guiding diagnostic algorithms to the correct diagnosis. Today, the gold
58 standard of routine diagnostic process relies on five methodological pillars: cytomorphology,
59 histology, chromosomal cytogenetics, immunophenotyping, and molecular genetic testing.
60 This leads to a treatment enabling diagnosis in the vast majority of cases. However,
61 approximately 10 % of cases remain unresolved from a diagnostic point of view and hence do
62 not lead to a satisfactory diagnosis according to current WHO standards (2017). We intend to
63 solve this issue to provide illuminating diagnostic guidance for the best possible patient's care.

64 2. Objectives

65 To address this problem, we hypothesize that novel high throughput sequencing methods, e.g.,

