66 whole genome and/or whole transcriptome sequencing are able – by virtue of painting a more
67 delicate genetic portrait of a tumor sample – to provide a more accurate diagnosis.
68 To this end we generated a reference collection of 5,500 samples with the full spectrum of
69 hematological malignancies, for which we performed whole-genome sequencing as well as
70 whole-transcriptome sequencing. Moreover, gold standard diagnoses according to WHO
71 classification with all needed techniques, all performed in MLL, clinical data and therapy
72 response data are fully available for these cases. The main advantage of this reference

73 collection consists of the unambiguity of each diagnosis, providing a reference framework for
74 any further classification and diagnosis especially in difficult cases.

75 Therefore, SIRIUS will compare the diagnostic superiority of WGS or WTS to the combined
76 approach with gold standard results and by matching the obtained results to the nearest “digital
77 sibling” within our reference cohort of more than 5,500 WGS and WTS (both in 93% of cases).

78 To this end, we will use an inhouse developed matching algorithm, which is able to match
79 genomic or transcriptomic profiles to a group of similar cases and gold standard results from
80 timepoint of this study. Current workflows intended to generate WTS/WGS data from patient
81 samples – all while fulfilling state of the art accreditation (ISO 15189) – require up to 5 – 7
82 days. This is largely comparable to classical methods but holds the promise to replace error
83 prone and arduous iterations in the methodological work up. The objective is to test whether
84 WTS and/or WGS based approaches can surpass classical methods regarding diagnostic
85 precision and routine reliability. Here we will test this hypothesis in a prospective real-world
86 setting under diagnostically difficult circumstances.

87 **II. STUDY DESIGN**

88 1. Type of Study

89 SIRIUS is conducted as a monocentric prospective case-control study. The study population
90 consists of carefully chosen patients with potential hematological malignancy, for which
91 current diagnostic methods were not sufficient to provide clear-cut diagnosis and definitive
92 clinical guidance. SIRIUS is entirely a non-interventional study without therapeutic
93 consequences for direct patient care. Data will be used as research study and micro-cost
94 analysis will be provided.

95 2. Duration of Study

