96 SIRIUS will be conducted for a total number of 110 patients with inconclusive diagnosis by
97 gold standard techniques for a total of up to nine months after the first enrollment. Patients to
98 qualify for study will be selected by referring center and PI before material is send to MLL.

99 3. Quality Control

100 Due to the heterogeneity in quality of blood and bone marrow samples arriving at MLL,
101 SIRIUS is preceded by a rigorous quality assessment of every patient history, data already
102 available and sample source and quality to be potentially included in the present study. The
103 minimal requirements are listed in III.

104 4. Primary Study Endpoints

105 Overall, the efficacy and supremacy of WGS/WTS analysis will be subjected to current
106 standard procedures. The primary endpoint will be assessed as follows: unclear cases will be
107 subjected to three diagnostic algorithms:

108 (1) Inhouse at referring site by histopathological diagnosis in the context of a hematological
109 tumor board according to current standards (“best practice”)

110 (2) Current gold-standard diagnostic workup as performed routinely by the MLL,
111 consisting of

112 a. Cytomorphological diagnosis
113 b. Immunophenotypic diagnosis
114 c. Chromosomal banding analysis
115 d. Molecular testing
116 e. NGS based Targeted panel sequencing

117 (3) WGS and WTS sequencing plus matching to nearest digital sibling in 5,5k cohort

118 The results of (2) and (3) arms will be first compared to the result obtained in (1) since this is
119 the therapy guiding approach *in domo*. Clinical follow-up observations will be made to assess
120 the success of this first diagnosis.

121 Next results from (2) and (3) will be compared against each other to obtain an assessment of
122 replaceability of current gold-standard methods to either WGS or WTS and WGS/WTS
123 combined. If both approaches do not yield a similar conclusion, specific data from (2) will be
124 added to results in (3) until a definitive assessment can be made.

125 5. Secondary Study Endpoints

126 • Turn-over time until potential therapy guiding diagnosis
127 • Cost-effectiveness until timepoint of diagnosis and therapy
128 • Compare WES to WGS data in SIRIUS cohort
129 • Identify number of potential actionable targets for which a therapy has been approved
130 but identification was missed in (1) and (2)
131 • Identify putative disease stage in comparison to (2) and clinical history

132

133

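### The first primary comparison, (2) and (3) against the referring-site result (1), can show added yield in unclear cases but not superiority over (1), because patients enter when prior work-up has fallen short

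*Protocol*

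**What the plan says.** **Aim.** II.4 begins "Overall, the efficacy and supremacy of WGS/WTS analysis will be subjected to current" standard procedures. I.2 asks whether "WTS and/or WGS based approaches can surpass classical methods regarding diagnostic" precision and routine reliability. The summary at the front of the protocol asks a different question, one of yield: "question of how often a better or final diagnosis can be delivered by WGS and/or WTS and if" unclear cases can be resolved.

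**Comparisons.** II.4 sends unclear cases through three algorithms: (1) the referring-site histopathological diagnosis with tumor board, described as following current standards; (2) the MLL gold-standard work-up; (3) WGS and WTS with matching to the reference cohort. The first comparison is "The results of (2) and (3) arms will be first compared to the result obtained in (1) since this is" the therapy-guiding approach. After that, (2) and (3) are compared with each other to judge replaceability. Where they disagree, (2) data are added to (3) until a definitive assessment is reached. Clinical follow-up is described for the success of the first diagnosis.

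**Entry.** II.1 describes patients for whom "current diagnostic methods were not sufficient to provide clear-cut diagnosis and definitive" clinical guidance. II.2 says "SIRIUS will be conducted for a total number of 110 patients with inconclusive diagnosis by" gold-standard techniques, and that patients who "qualify for study will be selected by referring center and PI before material is send to MLL". III.3 lists five sub-bullets, the first being an unclear diagnosis after internal routine work-up, and a separate criterion that the current work-up is not satisfactory.

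**Analysis.** IV assesses sensitivity and specificity of each method against the internal gold-standard work-up.

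**The concern.** A comparator whose shortfall is the reason for entry starts at a disadvantage. Cases that it handled well are not sampled, so they cannot count in its favour. A second method of the same overall quality will resolve some of the selected cases and appear better.

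II.4 places the whole primary endpoint under a supremacy aim and puts this contrast first. It does not say that the contrast with (1) is to be read as yield only. A sound yield result could therefore be reported as superiority over referring-site best practice. Follow-up of the first diagnosis does not remove the problem, because it takes place in the same selected patients.

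**Working it through.** The protocol gives no effect size, test or power for this comparison, so there is no figure to reproduce. The check is mainly one of design logic.

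**1. Which work-up failed?** Selection is by the referring center and the PI before material goes to MLL. The work-up known at that time is the referring site's, so it is most naturally (1). This is an inference: II.4 also says that unclear cases are subjected to (1), which could mean a new assessment after entry.

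**2. Direction.** Let both methods truly resolve a share p of this type of case, let rho be the correlation of their results, and let f be the share of enrolled cases in which (1) counts as resolved. All three are unknown.

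- New method resolves, given that (1) failed: p(1 − rho)
- New method fails, given that (1) resolved: (1 − p)(1 − rho)
- Net difference: (1 − f)p(1 − rho) − f(1 − p)(1 − rho) = (1 − rho)(p − f)

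With no selection on (1), f = p and the difference is 0. With selection against (1), f < p, and with rho below 1 the difference favours the new method although the two are equally good. This fixes the sign only. The documents supply none of the three inputs.

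**3. The clearest route.** Assume a resolved/unresolved score, which the protocol does not name, and a patient who entered because (1) gave no clear diagnosis. Then (1) is unresolved by definition and the other method can only tie or win. Exact McNemar p values with one discordant cell empty:

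- 5 versus 0: 2 × 0.5^5 = 0.0625
- 6 versus 0: 2 × 0.5^6 = 0.031

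Six cases are 6/110 = 5.5% of the planned sample. This describes one of the five III.3 sub-bullets. Under the others a diagnosis from (1) may already exist.

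**4. (3) versus (2).** Algorithm (2) consists of cytomorphology, immunophenotyping, banding analysis, molecular testing and panel sequencing, which are classical techniques of the kind whose insufficiency led to entry. Its results are likely to correlate with the failed work-up, so (2) may be depressed too. Two further constraints apply:

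- If the internal gold standard in IV is (2), then (2) has perfect sensitivity and specificity against itself, and (3) can at most tie.
- If (2) data are added to (3) before scoring, the disagreements that would carry a win for (3) are settled with (2)'s own data.

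**5. What the restated analysis could deliver** (illustrative counts, Wilson 95% CI):

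| Newly resolved | Proportion | 95% CI |
|---|---|---|
| 33 of 110 | 30% | 22.2–39.1% |
| 24 of 80 (larger entry group) | 30% | 21.1–40.8% |
| 9 of 30 (smaller entry group) | 30% | 16.7–47.9% |

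Paired example for (3) versus (2), with 20 resolved only by (3) and 8 only by (2): (20 − 8)/110 = 10.9 points. The standard error is √(28 − 12²/110)/110 = 4.70 points, the Wald 95% CI is 1.7 to 20.1 points, and the exact McNemar p is 0.036.

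**The case against.** The strongest reply is that no superiority claim over (1) is stated. The explicit superiority sentence in I.2 is worded against gold-standard results. II.4 gives a separate reason for comparing with (1), namely that it guides therapy, and the order first-then-next is not a hypothesis. The scope is also visible in the text: the summary asks about yield, and I.2 places the test in a "setting under diagnostically difficult circumstances". Enrolling unresolved cases is the purpose of the study.

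Much of this stands. A reader might infer that the protocol expressly claims superiority over (1). It does not; the link runs through the supremacy sentence in II.4 and the description of (1) as following current standards. But that sentence opens the primary endpoint, the contrast with (1) is its first comparison, and II.4 does not confine that contrast to yield.

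Three other strong readings are not supported:

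- That (1) scores zero in all 110 patients. Only the unclear-diagnosis sub-bullet implies this, and III.3 does not say how its sub-bullets combine.
- That II.2 contradicts itself by calling entry cases inconclusive by gold-standard techniques before MLL has the material. I.1 defines the gold standard generically as five pillars, so the phrase can describe work-up done elsewhere.
- That (3) versus (2) is free of the problem and can carry a general superiority claim. Step 4 of the working shows why it may not be.

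**Conclusion.** The point holds as a limit on interpretation. To the extent that entry depends on (1), comparing (2) and (3) with (1) is a valid measure of added yield in unclear cases and not a valid test of superiority over referring-site practice. The direction follows from the design if (1) is the pre-entry work-up, which is the natural reading but not a stated one. The size cannot be derived from the documents; it depends on the mix of entry routes and on a scoring rule that the protocol does not name. The 6 versus 0 figure shows how little is needed in one route and is not an estimate of the bias.

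The (3) versus (2) comparison may lean the same way through selection. Conversely, it cannot show (3) ahead if (2) is the reference standard or if (2) data enter (3) before scoring. Any conclusion from it applies to diagnostically unclear cases only.

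**What to change.** 1. In II.4, report (2) and (3) versus (1) as the proportion of unclear cases newly resolved, with a 95% CI. Report changed diagnoses separately. Make no superiority claim over (1).
2. State in II.4 whether (1) is the pre-entry diagnosis or a new one. Record at entry whether (1) gave no clear diagnosis or one judged unsatisfactory, and show the results by this item. The III.3 entry routes stay as they are.
3. Base (3) versus (2) on the (3) result locked before any (2) data are added. Do not use (2) as the reference standard for that comparison; use the WHO criteria and the clinical follow-up already planned, and say that this follow-up is read against all the results and not only the first diagnosis. Limit the conclusion to diagnostically unclear cases.

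**Cost.** Amendment wording, one entry item and a result lock. Patients, samples and tests do not change. The sponsor gives up a superiority claim over (1) and any claim beyond unclear cases. The smaller entry group will have a wide interval, as the 9 of 30 example shows.

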134 **III. SUBJECT SELECTION AND WITHDRAWAL**

135

136 1. Number Of Subjects

137 SIRIUS intends to enroll a total number of 110 cases provided by approximately 50 certified
138 hematological centers.

139

140 2. Gender, Age

141 Patients' samples from both sexes will be used (male and female). Only samples from adult
142 patients (18 years or older) will be used.

143

144 3. Inclusion Criteria

- 145 • Patients having been investigated with a suspected hematological disorder and:
 - 146 ○ Having unclear diagnosis after internal routine diagnosis
 - 147 ○ Unusual clinical course
 - 148 ○ Unusual r/r status or non-responder
 - 149 ○ Multiple parallel hematological conditions
 - 150 ○ Difficult/rare therapy associated/secondary neoplasms
- 151 • Current diagnostic work-up is not satisfactory in terms of (1) accuracy (2) clinical
152 behavior
- 153 • Only samples of patients min. 18 years of age will be used
- 154 • Material with a minimum of 20% tumor content in bone-marrow or peripheral blood
155 sample
- 156 • Samples must suffice quality attributes control which are denoted in (4.)
- 157 • Patient's informed consent

158 4. Exclusion Criteria

159 • Sample is not fit for state-of-the-art diagnosis, fails initial quality control. For quality
160 insurance we will exclude samples with wrong anticoagulant sent. Samples with
161 damage due to meteorological reasons (freeze-thaw damage or elevated temperature)
162 will be excluded.

163 • Samples with too scarce material jeopardizing routine gold-standard diagnosis will be
164 excluded (tumor content < 20 %).

165

166 5. Location

167 SIRIUS will be conducted as monocentric trial at the MLL.

168 **IV. STATISTICAL PLAN**

169

170 To determine the statistical significance within the endpoint analysis we will assess both
171 quantitative as well as qualitative variables. Quantitative variables will be described with the
172 number of non-missing values, mean, standard deviation, median, and minimum/maximum
173 values. Qualitative variables will be expressed as a number and percentage of patients with
174 each qualitative characteristic. The missing values are not intended to be included in the
175 calculation of percentages. Sensitivity and specificity will be assessed specific to each method,
176 with respect to internal gold standard diagnostic work-up.

177

178 **V. RISKS AND BENEFITS**

179 *Potential Direct Benefits to Subject*

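### The comparison with the referring-site diagnosis in II.4 does not fix specimen, disease episode or treatment state, so disagreement with (1) cannot be attributed to the method alone

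*Protocol*

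**What the plan says.** II.4 of the protocol sends unclear cases through three work-ups. Work-up (1) is described as "Inhouse at referring site by histopathological diagnosis in the context of a hematological" tumor board. Work-up (2) is the routine MLL gold standard, and (3) is WGS and WTS with matching to the reference cohort. The first step of the primary endpoint is then: "The results of (2) and (3) arms will be first compared to the result obtained in (1) since this is" "the therapy guiding approach *in domo*. Clinical follow-up observations will be made to assess" "the success of this first diagnosis". Only after that are (2) and (3) compared with each other.

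Eligibility bears on this pairing. III.3 requires that the diagnosis was unclear after the internal routine work-up. It also lists an unusual clinical course, "Unusual r/r status or non-responder", and therapy-associated or secondary neoplasms. The sample criterion is "Material with a minimum of 20% tumor content in bone-marrow or peripheral blood". II.2 says that patients who "qualify for study will be selected by referring center and PI before material is send to MLL". III.1 sets the size: "SIRIUS intends to enroll a total number of 110 cases provided by approximately 50 certified" centers.

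**The concern.** A paired comparison of diagnostic methods isolates the method only if both are applied to the same disease state, and ideally to the same material. II.4 does not secure this for (1). A refractory or non-responding patient has by definition been treated. If (1) is the diagnosis that guided that treatment, the MLL material may reflect a disease that has since progressed or changed clonally. If blood was sent, it is not the tissue that histopathology read.

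At stake is the interpretation of any gain over referring-site practice. I.2 aims to test whether sequencing can surpass classical methods in diagnostic precision. If such a statement rests on disagreement with (1) pooled over all cases, a reader cannot tell how much of it belongs to the method.

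**Working it through.** The protocol gives no figure on this point to reproduce: no expected disagreement rate, no share of treated patients and no interval between work-ups. The check is therefore mainly a reading of the text, followed by an illustration of scale.

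**What the text fixes**

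- *Sequence.* Entry follows the internal work-up (III.3), selection precedes shipment to MLL (II.2), and II.4 calls (1) therapy guiding and the first diagnosis. Together these put (1) ahead of (2) and (3).
- *Treated patients.* They are eligible under at least two III.3 criteria: relapsed/refractory or non-responding, and therapy-associated or secondary neoplasms.
- *Tissue.* (1) is histopathological; the MLL material may be peripheral blood.
- *Shared material for (2) and (3).* Both are run on what is sent to MLL, and section V gives routine diagnosis priority in the use of that material. The problem therefore lies with (1).

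**What the text leaves open**

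- The date of (1), the date on which the MLL material was drawn, and the longest interval allowed between them.
- Whether (1) is repeated at referral for a patient treated since the initial work-up.
- How a disagreement with (1) is scored.

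**Possible safeguards**

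- II.3 reviews history, available data and sample source, but as a quality check before entry. It points to section III for its minimum requirements, and none of those aligns (1) with the MLL sample.
- Disease stage appears in II.5, but only as a secondary endpoint, set against (2) and clinical history rather than against (1).
- Follow-up in II.4 judges how well (1) succeeded. A correct diagnosis followed by progression could look like a failed one, so follow-up alone does not separate the two.

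**Scale, for illustration only**

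Let *s* be the share of patients treated between (1) and the MLL sample, and *c* the probability that the disease changed enough in those patients to alter the diagnosis. Both are assumptions. The number of cases that differ from (1) through disease change alone is 110 × *s* × *c*.

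| *s* | *c* | Cases | Share of 110 |
|---|---|---|---|
| 10% | 5% | 110 × 0.10 × 0.05 = 0.55 | 0.5% |
| 25% | 20% | 110 × 0.25 × 0.20 = 5.5 | 5% |
| 50% | 30% | 110 × 0.50 × 0.30 = 16.5 | 15% |

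For comparison, the 95% half-width of a proportion at n = 110 is 1.96 × √(p(1 − p)/110). That is 5.6 percentage points at p = 10% and 9.3 points at p = 50%. The effect could thus be well inside sampling error or exceed it. Differences due to tissue alone are not in this sum.

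**The case against.** The strongest reply is that the text never says (1) is an old diagnosis. II.4 can be read as three work-ups done in parallel at referral, with (1) performed to current standards and then followed prospectively. A site may have repeated its work-up at relapse. II.2 says when material is shipped, not when it was drawn, so an aspirate taken alongside the biopsy would fit. This stands: a reader might infer that (1) usually predates therapy, but the protocol does not establish it.

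A reader might also infer that disease change is counted as a better diagnosis, and hence that the comparison favors (2) and (3). The documents do not support that either. II.4 says only that results are compared and contains no rule that turns disagreement into a gain, so no direction of bias follows. Nor does a time shift by itself give sequencing an advantage over the MLL gold standard, since both are set against the same (1).

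Two further arguments carry less weight. Data fields and stratification often sit in the case report form or the SAP, which is not shown. But the pairing and the eligibility are set in the protocol, and an SAP can stratify by sampling date or intervening therapy only if these are collected. It can also be said that dropping treated patients would undercut the real-world aim in I.2. That is a fair argument against exclusion, and separate reporting meets it.

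**Conclusion.** A limited point holds. II.4 applies the comparison with (1) to all cases without tying (1) to the specimen, episode or treatment state of the MLL material, while III.3 deliberately admits patients in whom these can differ. In such cases, disagreement with (1) cannot be attributed to the method alone.

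The direction and size of the effect cannot be determined from the protocol. The range of 0.5% to 15% of the cohort rests entirely on assumed shares and shows only that the effect may be negligible or material. If every referring site repeats its work-up at referral on concurrent material, little of the problem remains beyond differences in tissue; the protocol does not say so. The comparison of (2) with (3), which carries the question of replaceability, is largely untouched. This is an inexpensive improvement to the plan and does not invalidate the study.

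**What to change.** Record three items both for (1) and for the MLL sample: sampling date, specimen type, and whether therapy was given in between. The history and sample review in II.3 is a natural place to collect them.

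Add to II.4, for example: *The comparison of (2) and (3) with (1) is reported separately for pairs from the same disease episode without intervening therapy and for all other pairs; any claim of superiority over (1) rests on the former group.* Specimen type should be shown within each group, so that histology-versus-blood pairs can be seen. If (1) is meant to be a concurrent work-up at referral, II.4 should say so.

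The cost is three data fields and a smaller denominator for the claim against (1), with a correspondingly wider interval. All 110 cases stay in the study and in the comparison of (2) with (3).

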180 Conducting SIRIUS will not bear any risks for patients enrolled in the study. Normal State-of-
181 the-art diagnosis is provided for each sample and prioritization of sample material in favor
182 current diagnostic material and reporting is performed to prevent jeopardization of gold
183 standard diagnosis.

184

185 **VI. DATA HANDLING AND RECORD**

186 Data management documents will be generated under the responsibility of the Sponsor. A
187 management plan will be issued before data collection begins and will describe all functions,
188 processes, and specifications for data collection, cleaning, and validation. The data
189 management documents will describe analysis methods and individuals who are authorized to
190 enter the data, decisions about ownership of data, source data storage, the origin and destination
191 of the data and who will always get access to the data. Data Management Responsibilities are

192 primarily handled by co-investigator [name]. Per request of external researchers,
193 the Sponsor will provide these investigators with additional data relating to the trial, duly
194 anonymized and protected in accordance with applicable requirements.

195

196 **VII. STUDY MONITORING, AUDITING, AND INSPECTION**

197 The Investigator will make all the trial-related source data and records available at any time to
198 quality assurance auditor(s) mandated by the Sponsor, or to domestic/foreign regulatory
199 inspectors or representatives who may audit/inspect the trial. The main purposes of an audit or
200 inspection are to assess compliance with the trial protocol and the principles of ICH-GCP
201 including the Declaration of Helsinki and all other relevant regulations.

202

203 **VIII. FINANCIAL CONSIDERATIONS**

204 The MLL is the main sponsor of this trial. Reagents for gold standard investigations will be
205 provided by MLL. Reagents for sequencing will be provided for by Illumina®, Inc. San Diego,
206 CA. All Data generated are fully owned by MLL. MLL will share aggregated and anonymized
207 data with Illumina®, i.e., without revealing patient sensitive data such as germline mutations.

208

209 **IX. CONFLICT OF INTEREST**

210 [name]. phil. Dr. med. [name] and [name]. med. [name] are part owners
211 of the MLL Munich Leukemia Laboratory.

212

213 **PUBLICATION PLAN**

214 The results obtained from SIRIUS will analyzed according to the guidelines of Good scientific

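### Clinical follow-up is specified only for the referring-site diagnosis (1), so the plan has no common reference by which sequencing (3) could be shown to surpass the laboratory work-up (2)

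*Protocol*

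**What the plan says.** Protocol section II.4 puts each unclear case through three algorithms: (1) the referring site's histopathology and tumor board, (2) the central laboratory's gold-standard work-up, and (3) whole-genome and whole-transcriptome sequencing with matching to a reference cohort.

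- **First comparison:** "The results of (2) and (3) arms will be first compared to the result obtained in (1) since this is" the approach that guides therapy locally.
- **Follow-up:** "Clinical follow-up observations will be made to assess" "the success of this first diagnosis". The only natural referent is (1), named in the sentence before.
- **Second comparison:** "Next results from (2) and (3) will be compared against each other to obtain an assessment of" whether sequencing can replace the current methods. If the two conclusions differ, data from (2) are added to (3) until the case is settled.
- **Section IV:** sensitivity and specificity of each method are assessed "with respect to internal gold standard diagnostic work-up".
- **Section II.2:** "SIRIUS will be conducted for a total number of 110 patients with inconclusive diagnosis by" "gold standard techniques for a total of up to nine months after the first enrollment".

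Section I.2 states the objective as testing whether sequencing outperforms classical methods in diagnostic precision and routine reliability.

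**The concern.** To show that (3) is better than (2), both must be judged against something other than (2). Follow-up is the only source in the plan that does not come from one of the three diagnoses, and it is assigned to (1) alone. The laboratory work-up then serves both as comparator and, in section IV, as reference, in patients whom section II.2 describes as inconclusive by gold-standard techniques.

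Two things are at stake. In the section IV analysis, the cases that would demonstrate a benefit of sequencing are booked as its errors. In the head-to-head step, disagreement is resolved by merging (2) into (3), so the result no longer shows which of the two was right. If the separate diagnoses are not kept, that may not be recoverable afterwards.

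**Working it through.** The protocol gives 110 patients but no accuracy for any algorithm, so there is no stated figure to reproduce. The text settles the main point; the arithmetic only illustrates it.

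**Step 1. What each planned analysis uses as reference**

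| Place | Judged | Against | Follow-up used? |
|---|---|---|---|
| II.4, first comparison | (2) and (3) | (1) | Only indirectly |
| II.4, follow-up sentence | (1) | Clinical course | Yes |
| II.4, second comparison | (2) and (3) | Each other | No |
| II.4, disagreement rule | (3) with data from (2) added | Nothing named | No |
| IV, sensitivity and specificity | Each method | Internal gold standard | No |

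The secondary endpoint on disease stage in II.5 refers to (2) and to clinical history, which is not follow-up outcome. Section II.4 uses the term gold standard for (2), so (2) is the natural reading in section IV. If the word internal meant the referring site, the reference would be (1), which is still not an outcome.

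**Step 2. What agreement with (2) says about (3)**

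Let p2 and p3 be the probabilities that (2) and (3) are right (assumed), x the probability that both are right, and s the share of joint errors that carry the same wrong label (0 to 1).

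- Both wrong = 1 − p2 − p3 + x
- Agreement = x + s(1 − p2 − p3 + x)
- x lies between max(0, p2 + p3 − 1) and min(p2, p3)

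For p2 = 0.60 and p3 = 0.80:

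- Independent errors: x = 0.60 × 0.80 = 0.48 and both wrong = 0.40 × 0.20 = 0.08. Agreement is 0.48 to 0.56.
- Lowest: x = 0.40, both wrong = 0. Agreement is 0.40.
- Highest: x = 0.60, both wrong = 0.20, all with the same label. Agreement is 0.80.

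| p2 | p3 | Agreement, independent errors | Agreement, any dependence |
|---|---|---|---|
| 0.50 | 0.70 | 0.35–0.50 | 0.20–0.80 |
| 0.60 | 0.80 | 0.48–0.56 | 0.40–0.80 |
| 0.70 | 0.90 | 0.63–0.66 | 0.60–0.80 |

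The formula is unchanged if p2 and p3 are swapped. Agreement therefore cannot say which method is better, let alone how accurate (3) is.

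**Step 3. How far follow-up reaches through (1)**

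The expected number of cases with exactly one of (2) and (3) right, under independence, is 110 × [p2(1 − p3) + p3(1 − p2)]. For 0.60 and 0.80 this is 110 × (0.12 + 0.32) = 48.4. The other two pairs give 55.0 and 37.4.

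Let q be the probability that follow-up confirms (1), also assumed and taken as independent. Follow-up then supports whichever of (2) and (3) agrees with (1):

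| q | Settled through (1) | No outcome-based decision |
|---|---|---|
| 0.10 | 3.7–5.5 | 33.7–49.5 |
| 0.30 | 11.2–16.5 | 26.2–38.5 |
| 0.50 | 18.7–27.5 | 18.7–27.5 |

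Ranges run over the three accuracy pairs. A low q is plausible because section III.3 lists an unclear routine diagnosis among the inclusion routes.

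**The case against.** Several stronger readings are tempting, and the documents do not support them.

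- **That follow-up never touches (2) or (3).** The sentence before the follow-up sentence compares both with (1), so a confirmed (1) lends support to whichever agrees with it. This stands; the route is indirect and, on the figures above, partial.
- **That the primary comparison scores (3) as wrong whenever it departs from (2).** The head-to-head step is symmetric and sends disagreements on for further assessment. Only the sensitivity and specificity sentence in section IV has that effect.
- **That this is differential verification.** That term is for patients who receive different reference standards for the same test. Here each algorithm is handled alike in every patient.
- **That treatment in fact follows (2).** Section V says the routine work-up is provided for each sample, but II.4 names (1) as guiding therapy, and nothing says treatment changes.
- **That agreement understates the accuracy of (3) by a fixed 24–32 points.** That gap, 80% less 48–56%, needs independent errors. Section I.2 describes a reference cohort labelled by the same laboratory's gold standard, so correlated errors are plausible. Under any dependence the gap is 0–40 points. Overall agreement is also not the same quantity as sensitivity.

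Two further arguments carry weight. The second comparison asks about replaceability, for which agreement is a relevant measure. And follow-up is an imperfect referee: treatment is guided by (1), so the course under treatment guided by a discordant (2) or (3) is not seen, and patients enrolled late in a study of up to nine months may have little follow-up. A blinded panel diagnosis could serve instead, so follow-up is not the only possible reference.

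A statistical analysis plan or the data management documents might add adjudication rules. But the protocol does not leave the matter open: it assigns follow-up to (1) and names the section IV reference.

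**Conclusion.** The point holds in limited form. As written, follow-up assesses (1), reaches (2) and (3) only through agreement with (1), and is not consulted when (2) and (3) disagree. Sensitivity and specificity are taken against the internal gold standard. No common reference remains by which (3) could be shown to surpass (2), which is the objective in I.2.

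This conclusion rests on the text and on reading the follow-up sentence as referring to (1), not on any assumed figure. The sizes are illustrative only: agreement of 40–80% for assumed accuracies of 60% and 80%, and roughly 19 to 50 of 110 cases with exactly one method right but no outcome-based decision, across the assumed values.

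It should be fixed, but it does not invalidate the study. The design is non-interventional, the agreement results keep their value for the replaceability question, and the remedy uses follow-up that is already planned.

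**What to change.** Amend II.4 and section IV as follows.

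1. The diagnoses from (1), (2) and (3) are each recorded as first made, before any data from (2) are added to (3).
2. The planned follow-up is used to classify each of the three as confirmed, refuted or undetermined, at the same time point and by the same stated criteria.
3. The diagnosis on which treatment was based is recorded for each patient.
4. (3) is compared with (2) within patients on the confirmed proportion, and the undetermined share is reported for each. Undetermined is an outcome category and not a missing value, because section IV leaves missing values out of percentages.
5. The analysis against (2) is described as agreement, not as sensitivity, specificity or accuracy.

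The cost is a protocol amendment and two further classifications per patient. The protocol shows no follow-up schedule or form, so the exact burden cannot be stated; a time point and criteria would have to be set. The downside is that some cases will stay undetermined, given a study of up to nine months and treatment guided by (1). Follow-up remains an imperfect reference, and the report should say so.
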